COVER PAGE

NCT06079853

Date of Protocol Approval: 10/18/2023

Study Title: The Use of Physiologic Measures and Sleep Health Promotion to Identify and Mitigate Predisposing Factors of Suicidal Ideation in Nurses

PI: [name], RN, ANP-BC, FAAN

PI Contact: [contact]

Sponsor: Columbia University School of Nursing

STUDY PROTOCOL

The purpose of this study is to generate longitudinal pilot data that investigates 1) which factors (stressful life events, psychiatric characteristics, and work environment characteristics) are associated with stress and subsequent suicidal ideation; and 2) to explore the preliminary impact of an existing evidence-based sleep intervention, *Somni*^{®14}, on stress, psychological health, and suicidal ideation in working nursing professionals. The specific aims are:

Aim 1. To investigate associations between sleep, stressful life events (life stressors, discrimination, lateral violence), psychiatric characteristics (psychiatric diagnosis, subjective mood), work environment characteristics (workload, shift type and duration, overtime, nurse work environment, and team relations) and stress (self-reported and heart rate variability) in working nursing professionals while controlling for standard covariates known to influence stress. *Hypothesis 1:* Suboptimal work environment characteristics are positively associated with self-report and physiologic indicators of stress [heart rate variability (HRV)]. *Hypothesis 2:* Poor sleep (duration and quality) will be positively associated with self-report and physiologic indicators of stress (HRV).

Aim 2. To determine if stress exposure (self-report and HRV) are associated with predisposing factors (sleep, stressful life events, additional psychiatric characteristics, and work environment characteristics), and to explore whether stress mediates the effect of predisposing factors on suicidal ideation in working nursing professionals. *Hypothesis:* Nurses with low HRV are at higher risk for suicidal behavior when exposed to poor sleep, the presence of psychiatric characteristics (e.g. Depression), stressful life events, or suboptimal work environment characteristics (e.g., poor team relations).

Exploratory Aim. To explore the preliminary impact of an existing sleep intervention (*Somni*[®]) on self-reported stress, HRV, sleep, and psychiatric health outcomes including depression, burnout, and suicidal ideation.

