Aim 2. We will classify nurses into quartiles of high (top 25%), medium (middle 50%), and low (bottom 25%) HRV. We will use descriptive statistics to examine individual measures and composite scores of factors (sleep, stressful life events, psychiatric characteristics, work environment characteristics) and suicidal behavior [C-SSRS score]. To evaluate the change in suicidal ideation over time and the impact of each factor composite score, we will fit conditional latent growth curve models using 3 data points. The models will be expressed such that, given mean HRV and baseline composite scores for each factor category: $y_{it} = (\mu_a + \mu_\beta \lambda_t + \gamma_1 HCC_i + \gamma_2 WEC_i) + (\zeta_{ai} + \zeta_{\beta i} \lambda_t) + \varepsilon_{it}$ where y_{it} is the C-SSRS score for nurse i at time t , μ_a is the latent variable for the intercept value (baseline score), μ_β is the random latent variable for slope (growth over time) for nurse i multiplied by the vector of factor loadings specifying time, λ_{it} , ε_{it} is the time-specific residual for nurse i , ζ_{ai} and $\zeta_{\beta i} \lambda_t$ are random components of the latent intercept and slope variables, respectively. Sleep, stressful life events and psychiatric characteristics are fixed (time-invariant) predictors. The factor loadings for time on slope can be fixed to adjust for gaps in outcomes, which would allow for modeling more distant (e.g., 2025) data from baseline without increasing the number of timepoints included in the model. Further, we anticipate fluctuations in HRV over time. To accommodate the change in trend, we will explore both linear and quadratic growth functions. Baseline global sleep scores (PSQI), stressful life events, psychiatric and work environment characteristics will serve as predictors of suicidal ideation change over time. Individual nurse characteristics and psychiatric characteristic controls will be included as an interaction term to compare curves across nurses. To explore whether stress mediates the effect of predisposing factors on suicidal ideation, we will compare the models assessing the effect of predisposing factors on suicidal ideation with and without the mediator outlined by Barron and Kenny difference method which be used to gauge the size of the mediation effect.

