Aim 3. We will calculate descriptive statistics, percentages, and frequencies for 1) each *Somni*[®] sleep kit component 2) subjective sleep quality via *Somni*[®] app 3) global sleep scores (PSQI score) and HRV. We will test differences in global sleep scores (PSQI), mean sleep duration (Oura ring), mean subjective sleep quality and use of sleep kit components at the individual level between the 3 data points. We will report the effect sizes and will test for significance in the model for each psychosocial and work environment factor, each *Somni*[®] sleep kit component (mean weekly frequency), and the mean PSQI score while controlling for age, sex, gender, race, and history of psychiatric diagnosis. We will repeat the same analysis modeling mean C-SSRS as the dependent variable. To evaluate the change in suicidal behavior over time and the impact of global sleep (PSQI score) and each *Somni*[®] sleep kit component (mean weekly frequency), we will fit conditional latent growth curve models.

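### The Aim 2 growth-curve equation has no predictor-by-time term, so as printed it cannot estimate the factor effects on change in suicidal ideation that the Aim 2 text promises

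*Combined protocol and SAP*

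**What the plan says.** STATISTICAL ANALYSIS, Aim 2, plans conditional latent growth curve models for the C-SSRS score at three surveys (baseline, Week 4, Week 8). The models are to be expressed "given mean HRV and baseline composite scores for each factor category". The four categories (sleep by PSQI, stressful life events, psychiatric, work environment) "will serve as predictors of suicidal ideation change over time".

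The predictor part of the equation is "\gamma_1 HCC_i + \gamma_2 WEC_i". The explanatory clause after it defines the outcome, the latent intercept and slope, the time loadings, the residual and the random components. It does not define HCC, WEC or the two gammas.

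The same paragraph adds three things that the equation does not show:

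- On curve shape: "we will explore both linear and quadratic growth functions".
- On interactions: "Individual nurse characteristics and psychiatric characteristic controls will be included as an interaction term to compare curves across nurses".
- On mediation: factor effects on suicidal ideation are to be compared in models with and without the stress mediator, by a difference method. Table 1 measures stress by both self-report and HRV.

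The hypothesis under Aim 2 in the specific aims begins: "Nurses with low HRV are at higher risk for suicidal behavior when exposed to poor sleep". For HRV groups, the analysis text says: "We will classify nurses into quartiles of high (top 25%), medium (middle 50%), and low (bottom 25%) HRV". Only descriptive statistics follow from that grouping.

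**The concern.** The equation and the prose describe different models. In the prose, four factors act on the trajectory, given HRV. In the equation, two unnamed quantities shift its level only. WEC is presumably the work environment composite; HCC matches no variable in Table 1.

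An analyst who fits the equation will see a factor that predicts worsening only as a constant level difference, plus a time trend shared by all nurses. An analyst who follows the prose must decide which predictors get slope terms, whether HRV does, and what the interaction multiplies. Two competent analysts could therefore report different models. This is the only growth-curve equation in the plan. Aim 3 uses the same model type for suicidal behavior and prints none, so it inherits the gap. The pilot is meant to inform a fully powered study, so the error could carry forward.

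**Working it through.** **1. Expected change under the printed equation (algebra, no assumptions).**

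E[y_it] = μ_a + μ_β λ_t + γ1 HCC_i + γ2 WEC_i.

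Subtracting two time points gives E[y_i,t2 − y_i,t1] = μ_β (λ_t2 − λ_t1). HCC and WEC cancel. The exposed-minus-unexposed difference in change is exactly 0 whatever γ1 and γ2 are.

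With added terms δ1 HCC_i λ_t + δ2 WEC_i λ_t, expected change becomes (μ_β + δ1 HCC_i + δ2 WEC_i)(λ_t2 − λ_t1), which depends on the factors.

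**2. What the printed equation would return (illustration).** Assumed inputs: a binary factor raises C-SSRS by 0, 0.5 and 1.0 points at Weeks 0, 4 and 8 (0.125 per week); intercept variance 1; residual variance 0.5. A generalized least squares fit on (1, t, factor) gives:

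| Assumed slope variance | Flat factor effect reported |
|---|---|
| 0 | 0.50 |
| 0.01 | 0.305 |
| 0.03 | 0.171 |

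The common slope is 0.125 × the exposed share: 0.031, 0.0625 or 0.094 per week at 25%, 50% or 75% exposed. A true difference in change is thus split between a level effect and a trend given to everyone.

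**3. Where the mediator must enter.** Assumed inputs: half of nurses exposed; low HRV in 35% of exposed and 15% of unexposed; low HRV raises C-SSRS by 0.125 per week; the factor acts on change only through HRV; variances as in step 2; complete data at all three surveys.

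| Model | Factor slope per week | Share of change reported as mediated |
|---|---|---|
| Without HRV | 0.125 × (0.35 − 0.15) = 0.025 | – |
| HRV on intercept only | 0.025 | 0% |
| HRV on intercept and slope | 0 | 100% |

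The result is the same for slope variance 0, 0.01 or 0.03. The true answer here is 100%. With complete data, an intercept-only mediator leaves the factor's slope coefficient where it was.

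**4. Quadratic growth.** A random quadratic needs 6 random-effect variances and covariances plus at least 1 residual variance, which is 7. Three time points supply only 6 variances and covariances, so it is not identified. A fixed quadratic can be fitted but uses up all three time-point means.

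**5. Secondary: moderation by HRV.** Assumed inputs: the 35%/15% split, single outcome, factor adds 1.0 point in low-HRV nurses and 0 in the rest.

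- Without HRV, the factor effect is 0.35.
- With HRV added but no interaction, the effect is a weighted mean of the two within-class effects. The weights are P(class) × variance of exposure in the class: 0.25 × 0.70 × 0.30 = 0.0525 for low HRV, and 0.75 × 0.433 × 0.567 = 0.184 for the rest. The effect is 0.0525 / 0.2367 = 0.22.
- The difference method reports 0.35 − 0.22 = 0.13, or 37%, as mediated.
- A truth with no interaction (0.22 for the factor, 0.64 for low HRV) gives the same figures. The additive comparison cannot tell the two apart.
- At splits of 30%/20% and 40%/10%, the mediated share is 19% and 55%.

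**6. Secondary: HRV window.** STUDY DESIGN component 3 collects physiologic data in Weeks 1–8; component 4 runs the intervention in Weeks 4–8. An average over all eight weeks includes 4/8 = 50% or 5/8 = 62.5% intervention weeks, depending on whether Week 4 counts.

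**The case against.** **The intent is clear.** The text names conditional growth curves, calls the factors predictors of change and speaks of comparing curves across nurses. A reader might infer from the equation that the plan as a whole rules out factor effects on change. The documents do not support that: the prose says the opposite, and the defect lies in the equation. What remains is that the prose does not say which coefficients sit on the slope, whether HRV does, or what the interaction multiplies.

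**The equation was read from PDF by a program.** Notation does vary (λ_t in one place, λ_it in another), and a lost symbol cannot be excluded. But the equation parses fully, λ_t appears on both slope terms, and the readable definitions omit HCC and WEC.

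**The missing quadratic is no contradiction.** This stands. The text says only that the quadratic will be explored, so a linear base equation is compatible with it.

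**The hypothesis concerns mediation.** A reader might infer that the Aim 2 hypothesis has no test at all. That goes too far. Aim 2 names mediation as an objective, and a comparison with and without the mediator is planned. An additive reading would be partly addressed by a model that includes mean HRV. Only if the wording means that a factor's effect depends on HRV is there no test. The HRV classes lead only to descriptive statistics, and the one interaction in the text does not mention HRV. Descriptives by class could show such a pattern informally, which in a pilot is worth something.

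**The HRV window is partly guided.** Component 4 names Weeks 1–4 as the comparison period for the intervention. That helps, but it does not fix the window for mean HRV in Aim 2.

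**Conclusion.** The equation is wrong as written and should be fixed; confidence is high. It contradicts the text on which predictors enter, on the presence of HRV, and on whether predictors act on change. Its consequence is an effect on change of exactly zero for every factor.

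Only that zero and the week counts follow from the documents. The flat effects of 0.17 to 0.50, the 0.025 slope and the 19% to 55% mediated shares rest on assumed effects, variances and exposure splits. They show how the models behave and do not predict this trial's bias.

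The moderation point is secondary and of moderate confidence, because it depends on one of two readings of the hypothesis. The HRV window is a missing detail.

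**What to change.** 1. **Correct the equation.** Replace HCC and WEC with defined terms for the four baseline composites, each entered as (γ_ak + γ_bk λ_t) x_ki. Joint entry follows the text. One factor at a time is a fallback if the sample is too small; such models do not adjust the factors for each other.
2. **Place the mediator.** In the with-mediator model, enter mean HRV, and likewise self-reported stress, on both intercept and slope.
3. **Define the interaction.** List the characteristics and state what they multiply. Characteristic-by-time is one reading, and the sponsor must choose. Do not enter the psychiatric composite twice.
4. **Quadratic.** If explored, use a fixed term only.
5. **Hypothesis.** State whether moderation by HRV is meant. If so, add one HRV-by-factor term per factor, using one stated form of HRV, and name the coefficient in advance. If not, reword the hypothesis.
6. **HRV window.** State the weeks averaged. Weeks 1–3 precede the intervention; Week 4 does too only if the intervention starts after the Week 4 survey.
7. **Aim 3.** Write out its growth-curve model in the same form.

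**Cost.** Wording and model terms; no new data. The printed equation has 2 predictor coefficients. The corrected joint model has 4 × 2 = 8 without the mediator and 10 with HRV on intercept and slope. One factor at a time, the counts are 2 and 4. All are before the nurse and psychiatric terms, whose number the plan does not give. Self-reported stress needs its own model or 2 more coefficients.

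Precision will be limited. If the factor is unrelated to HRV, a low-versus-rest HRV interaction has 1/√(0.25 × 0.75) = 2.3 times the standard error of the factor's main effect. The documents supplied give no sample size; at an assumed 30, 50 or 100 nurses, the low-HRV class holds about 8, 13 or 25. Four independent interaction tests at 0.05 carry a 1 − 0.95^4 = 18.5% chance of at least one false positive. Report estimates with 95% confidence intervals as exploratory.

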STUDY DESIGN. This study is a prospective pragmatic pilot trial to generate data needed to inform a fully-powered longitudinal study consisting of nurses across a wider geographic region. There are 4 study components:

1. Electronic Quantitative Surveys (baseline, Week 4 & Week 8) will consist of demographic questions and validated measures for personal characteristics, sleep, stressful life events, psychiatric characteristics, work environment factors, and all psychological health outcomes. (**Table 1**). The surveys will be administered 3 times (baseline, week 4 and week 8) to generate pilot longitudinal data.

2. Psychological Assessment (baseline). To confirm a preexisting psychiatric diagnosis, a *Structured Clinical interview for DSM-5 Diagnosis* (Research version) (SCID-5-RV) will be administered in-person by a Psychiatric Mental Health Nurse Practitioner (PMHNP) at baseline. SCID-5-RV is a semi-structured interview guide for making major DSM-5 diagnoses such as mood disorders, psychotic symptoms, substance use, sleep, and trauma- or stressor-related disorders and takes approximately 45-60 minutes to administer. Studies suggest that prior history of mental illness, such as depression, has been linked to suicide.

3. Physiologic Biomarkers (Weeks 1-8). Heart rate and sleep (hours/day) will be collected using a wearable device, *Oura ring*[®], a piece of jewelry that can be custom fit to each participant. Heart rate variability (HRV), a highly sensitive physiologic metric for stress, is the constant variation in milliseconds between beats, and controlled by the autonomic nervous system. Low HRV is a strong indicator of physiologic stress (fight or flight response) and has been associated with increased risk for suicide attempt. Studies have demonstrated high validity in the assessment of HRV and sleep using the *Oura ring*[®]. The device will also collect activity levels (steps/day) and sleep cycles, known confounders for stress levels.

TABLE 1. Study Variables and Measures

Variable	Operational Definition	Measure
Demographics	Age, Sex, Gender, Race, Ethnicity, marital status, household income, parental status, smoking history, substance use; years of nursing experience	Validated single-items
Sleep	Sleep quality and duration	Pittsburgh Sleep Quality Index ⁴⁴ ($\alpha = .83$) Oura ring [®] Somni [®] 14
Stress	Self-reported stress Heart Rate Variability	Perceived Stress Scale ⁴⁵ ($\alpha = .76$) Oura ring [®]

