4. Sleep Intervention (Weeks 4-8) *Somni*[®] is an evidence-based personalized sleep intervention aimed at promoting optimal sleep health and has demonstrated effectiveness in shift workers outside the healthcare sector (e.g. Disney). *Somni*[®] consists of a sleep kit and a smart phone application. The sleep kit is box of items with demonstrated past evidence of improving sleep health: Blue light blocking glasses, white noise machine, lavender spray, ear plugs, light blocking eye mask, and herbal tea. Rather than dictate a “one size fits all” approach to optimize sleep health, there is current evidence that individualized sleep interventions are recommended to optimize sleep quality. *Somni*[®] permits individualized sleep quality promotion and participants are able to select their preferred use, timing, and duration of each of the box contents. The kit is accompanied by a *Somni*[®] smartphone app that prompts participants to input the use of each component in the kit and provide a subjective sleep quality rating each day. Drs. [name] and [name] have partnered with the developers of *Somni*[®] who will provide free sleep kits and app access to our study participants. The *Somni*[®] app is interoperable with the *Oura Ring*[®] and will automatically sync all physiologic and sleep data together in one location, fully accessible to the participants, and displayed in graphs in the *Somni*[®] app that are easy to read and interpret (e.g. total daily steps; daily sleep hours). *Somni*[®] will be implemented Weeks 4 through 8 to investigate its preliminary impact on stress and suicidal ideation by comparing survey and physiologic metrics from Weeks 1-4.

STATISTICAL ANALYSIS

First, we will calculate composite scores of individual measures (sleep, stressful life events, psychiatric characteristics, and work environment characteristics). Descriptive statistics will be calculated including means

and standard deviations (normally distributed values), median and interquartile range (non- normally distributed variables), or absolute and relative frequencies (categorical variables). Outliers and missing data will be assessed (outliers > 3 standard deviations from the mean will be removed). Significance level will be set at $\alpha = 0.05$.

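### Aim 3 tests kit use and app sleep ratings across three time points although neither has a baseline value, and relates self-selected kit use to undefined mean scores with no pre-kit score among the listed controls

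*Combined protocol and SAP*

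**What the plan says.** **Schedule.** Study Design, component 1: "The surveys will be administered 3 times (baseline, week 4 and week 8) to generate pilot longitudinal data". Component 3 covers the ring: "Physiologic Biomarkers (Weeks 1-8). Heart rate and sleep (hours/day) will be collected using a wearable device". Ring sleep and heart rate variability (HRV) therefore have values before the kit is issued.

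**Kit and app.** Component 4 introduces them together. The app prompts participants to "input the use of each component in the kit and provide a subjective sleep quality rating each day". The kit holds six items: "Blue light blocking glasses, white noise machine, lavender spray, ear plugs, light blocking eye mask, and herbal tea". Nurses decide how to use them: "participants are able to select their preferred use, timing, and duration of each of the box contents". Somni is to be "implemented Weeks 4 through 8 to investigate its preliminary impact on stress and suicidal ideation by comparing survey and physiologic metrics from Weeks 1-4".

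**Aim 3 of the Statistical Analysis** (the Exploratory Aim of the opening section). Alongside PSQI and ring sleep duration, it tests "mean subjective sleep quality and use of sleep kit components at the individual level between the 3 data points". It then models mean weekly frequency of each kit component, psychosocial and work environment factors, and a mean PSQI score. The controls are age, sex, gender, race and psychiatric history. The same analysis is repeated with mean C-SSRS as dependent variable, and growth curves are fitted for suicidal behavior.

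**Aim 2**, by contrast, uses a pre-kit sleep score: "Baseline global sleep scores (PSQI), stressful life events, psychiatric and work environment characteristics will serve as predictors of suicidal ideation change over time".

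**The concern.** Two of the four variables in the three-point test cannot be observed at one of the three points. A significant difference in kit use between baseline and Week 8 would say nothing about sleep or suicidal ideation.

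The kit-use regressions have a different weakness. Nurses choose how much to use each item, and prior sleep is an obvious reason to choose. If poor sleepers use the kit more, use will look harmful or ineffective. If motivated, better sleepers use it more, use will look helpful. The natural protection is a pre-kit score in the model, and none is listed. Averaging scores from before and after kit use would add dilution to that confounding.

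The pilot is meant to inform a fully powered study. A kit-use estimate that may be diluted, or biased in an unknown direction, is poor material for that purpose.

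**Working it through.** The plan states no sample size, effect size or SD for Aim 3, so there is no figure to reproduce. The check sets the schedule beside the analysis and then illustrates the possible size.

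**1. What exists at each point**

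| Variable | Baseline | Week 4 | Week 8 |
|---|---|---|---|
| PSQI, C-SSRS | yes | yes | yes |
| Ring sleep, HRV | from Week 1 | yes | yes |
| App sleep rating | none | start of Somni at most | yes |
| Kit use | zero by construction | start of Somni at most | yes |

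Table 1 lists Somni as a sleep measure without timing, but nothing places app ratings before Week 4. Aim 3 does not define its three data points. Reading them as the three surveys follows from the schedule and from Aim 2, which fits growth curves to three data points.

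**2. Outcome of the first model.** The sentence naming mean PSQI does not say whether it is outcome or predictor. The next sentence repeats the analysis with C-SSRS as dependent variable, which implies that PSQI is the first outcome. If it is only a predictor, the first model has no stated outcome. A mean PSQI term in the C-SSRS model supplies a pre-kit sleep score only if that mean leaves out Week 8.

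**3. Dilution.** With a kit effect *b* at Week 8 only, the three-survey mean carries (0 + 0 + *b*)/3 = *b*/3.

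**4. Selection.** The inputs are assumptions; the documents give none of them. They are between-survey correlation *r* = 0.7, correlation *s* of kit use with the Week 4 score of −0.3, 0 or +0.3, and true effect *b* = −0.30 SD per SD of use, at Week 8 only. For one kit item and no other covariates:

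- Three-survey mean: *s*(1 + 2*r*)/3 + *b*/3. At *s* = +0.3: 0.3 × 0.8 − 0.10 = +0.14.
- Week 8, no pre-kit score: *sr* + *b*. At *s* = +0.3: 0.21 − 0.30 = −0.09.
- Week 8, adjusted for baseline: *rs*(1 − *r*)/(1 − *r*²*s*²) + *b*. At *s* = +0.3: 0.063/0.9559 − 0.30 = −0.23.
- Week 8, adjusted for baseline and Week 4: *b* = −0.30.

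| Model | *s* = −0.3 | *s* = 0 | *s* = +0.3 |
|---|---|---|---|
| Three-survey mean | −0.34 | −0.10 | +0.14 |
| Week 8, no pre-kit score | −0.51 | −0.30 | −0.09 |
| Week 8, baseline-adjusted | −0.37 | −0.30 | −0.23 |
| Week 8, baseline and Week 4 | −0.30 | −0.30 | −0.30 |

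**5. How the size shrinks.** If covariates explain a share *q* of each score, the three-survey estimate is *s*((1 + 2*r*)/3 − *q*)/(1 − *s*²*q*) + *b*/3. At *s* = +0.3:

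- *q* = 0.2: 0.18/0.982 − 0.10 = +0.08.
- *q* = 0.5: 0.09/0.955 − 0.10 = −0.006.

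With all six items in one model (inter-item correlation 0.3, selection 0.3 on each, one effective item, no other covariates), the bias is divided by 1 + 5 × 0.3 = 2.5. The three-survey mean then gives 0.24/2.5 − 0.10 = −0.004.

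Simulations with no true effect, *s* = 0.3 and controls explaining 20% used the three-survey mean at a nominal 5% level. At assumed sample sizes of 30, 50 and 100, one item is rejected in 20%, 35% and 64% of runs. With six items, the rate per item is 7%, 9% and 14%.

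**6. Limits of adjustment.** If half the effect is already present at the Week 4 survey, adjusting for both surveys gives *b*(1 − 0.5*r*/(1 + *r*)) = −0.30 × 0.794 = −0.24. Selection of 0.3 on a stable trait also leaves −0.24.

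**The case against.** The strongest reply is that the main Somni evaluation does not depend on these models. PSQI and ring sleep have pre-kit values, and Aim 3 compares them over time. Component 4 separately plans a comparison of survey and physiologic metrics with Weeks 1 to 4. The C-SSRS growth curve has a latent intercept that partly represents the starting level. What remains is secondary regression within an exploratory aim of a pilot. All of this stands, and it limits the reach of the point.

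A reader might infer that stress, HRV, depression and burnout have no planned before-after comparison, because Aim 3 gives HRV descriptive statistics only and names no test of change for the other scales. The documents do not support that. The component 4 comparison covers survey and physiologic metrics, and the surveys carry all the psychological outcomes. The comparison is thinly specified, and Week 4 can be counted in both windows, but it is planned.

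A reader might also infer that the kit-use estimate would reverse sign. That needs a three-survey mean, which the plan does not state, together with one item per model, limited covariates and positive selection. With six items together, or covariates explaining half of each score, the illustrated estimate is about zero and not reversed. The plan does not say whether the items and psychosocial factors share one model.

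The reply does not touch the missing baseline values, the undefined means, or the absence of a pre-kit score from the listed controls.

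**Conclusion.** The point holds on the text. The three-point test of app ratings and kit use has no baseline data beyond a structural zero for use. The kit-use models have undefined mean outcomes, a self-selected exposure and no listed pre-kit score.

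The reduction to one third is exact if all three surveys are averaged and the effect appears only at Week 8. The size and direction of selection bias are not determinable from the documents; the figures above are illustrations under stated assumptions. PSQI has no growth model to fall back on, so its kit-use association is the more exposed of the two.

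This should be corrected because it affects how the pilot's kit-use results can be read. It does not undermine the Somni before-after comparison.

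**What to change.** 1. Summarise kit use and app ratings within the Somni weeks only. Keep the time-point comparison for PSQI. For ring sleep and HRV, compare Somni weeks with earlier weeks, assign Week 4 to one window, and report 95% confidence intervals. This also avoids having to define a ring baseline when ring data begin in Week 1.
2. In the kit-use models, name the Week 8 PSQI or C-SSRS score as the outcome and adjust for that measure's baseline score in every nurse. This is the main model. Add the Week 4 score in a sensitivity analysis limited to nurses whose Week 4 survey preceded first kit use.
3. Label the kit-use associations exploratory and non-causal. Baseline adjustment reduces selection bias without removing it: in the illustration about 0.07 SD remains, against 0.21 SD for Week 8 with no pre-kit score.

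Cost: changes to the analysis wording, one or two degrees of freedom in a small pilot, and a check of survey dates against first kit use. No extra visits or surveys are needed.

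### Aim 3 tests ring sleep at three survey points, but the ring has no reading at the baseline survey, and no contrast with a trend check is set at the start of Somni

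*Combined protocol and SAP*

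**What the plan says.** - **Survey times.** Study Design, component 1: "The surveys will be administered 3 times (baseline, week 4 and week 8").
- **Ring.** Study Design, component 3: "Physiologic Biomarkers (Weeks 1-8). Heart rate and sleep (hours/day) will be collected using a wearable device". No ring reading before Week 1 is described.
- **Somni.** Study Design, component 4: the intervention "will be implemented Weeks 4 through 8", and its impact on stress and suicidal ideation is to be examined "by comparing survey and physiologic metrics from Weeks 1-4".
- **Analysis.** Statistical Analysis, Aim 3: "We will test differences in global sleep scores (PSQI), mean sleep duration (Oura ring), mean subjective sleep quality" and kit use, all "at the individual level between the 3 data points". The form of the test (omnibus or pairwise) is not named.

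The plan does not say which nights form each ring mean, what stands for ring sleep at the baseline point, or to which period Week 4 belongs. No comparison group is described. The Aim 3 models adjust for personal characteristics and psychiatric history, with no term for study time in the ring analysis. Growth curves are planned for suicidal ideation and behavior, not for ring sleep. HRV is an outcome of the Exploratory Aim, but in Aim 3 it is listed for description and not among the differences to be tested.

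**The concern.** One of the three points has no ring value, so the test cannot be run without a choice that the plan does not make. An analyst might use the first week of wear, drop the point, or average whole periods. Each choice answers a different question.

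The test also does not match the aim. A difference among three points can be significant because of a change between baseline and Week 4, before Somni could have acted. The Exploratory Aim asks what happened once Somni began.

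Without a comparison group, the weeks of wear before Somni are the main internal check on whether sleep was already changing. The plan collects those nights but does not use them for that purpose. It does expect movement over time: the Aim 2 text anticipates that HRV will fluctuate. Because the pilot is meant to inform a fully powered study, a drift mistaken for a Somni effect would carry into that study's planning.

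**Working it through.** The documents give no sample size, SD or effect size for this analysis, so there is no stated figure to reproduce.

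**Inputs from the documents.** Eight weeks of ring wear (8 × 7 = 56 nights if every night is recorded); Somni starting somewhere in Week 4; alpha 0.05, taken as two-sided.

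**Assumed inputs.** Drift of 1 to 3 minutes per week; 50 nurses; night-to-night SD 75 minutes; between-nurse SD of the true change 30 minutes; independent nights; full wear; one trend common to all nurses.

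**1. Size of the drift effect.** False difference = weekly drift × gap between period midpoints.
- Start on day 29 (28 nights before, 28 after): midpoints at nights 14.5 and 42.5, a gap of 28 nights = 4.0 weeks.
- Start on day 22 (21 before, 35 after): midpoints at nights 11 and 39, again 4.0 weeks.
- Seven-night windows at Weeks 4 and 8: also 4.0 weeks.
- Result: 1, 2 or 3 minutes per week gives 4, 8 or 12 minutes. This does not depend on the sample size or the SDs.
- If Week 1 stood in for the missing baseline, Week 8 minus Week 1 would span 7 weeks: 7 to 21 minutes.

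**2. How often drift alone would be significant.** For a 28 + 28 night contrast:
- SE = √[(30² + 2 × 75²/28)/50] = √[(900 + 401.8)/50] = 5.10 minutes.
- 4/5.10 = 0.78 and 12/5.10 = 2.35. Against 1.96, a true null is rejected 12% and 65% of the time (normal approximation).
- With a different assumption, an SD of 40 minutes for the change in period means, the rates at 1, 2 and 3 minutes per week are 7%, 14% and 25% with 20 nurses, and 12%, 33% and 63% with 60.

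**3. Cost of adjusting for trend.** With a linear trend in the model, the night-level variance of the level change at the start is 4.0 times as large, with or without a slope-change term (least-squares design, 28 + 28 nights).
- SE = √[(900 + 4 × 401.8)/50] = √(2507.1/50) = 7.08 minutes.
- Under a linear drift the bias of this estimate is 0.

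**4. Limits of trend adjustment.** Noise-free series were fitted to the same 56 nights, with the start after night 28. The entries are the estimated change in minutes.

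| Assumed pattern | Before/after means | Step with one common trend | Level change with trend and slope change |
|---|---|---|---|
| Real gain rising from 0 to 20 over the Somni weeks | 10.4 | 0.4 | 0.7, with slope change 5.0 per week |
| Real gain reaching 20 in two weeks, then flat | 15.4 | 5.9 | 6.2, with slope change 4.7 per week |
| No gain; 20-minute early deficit fading with a 3-night time constant | 2.5 | −3.4 | −3.6, with slope change −3.0 per week |

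A step with one common trend nearly misses a gradual real gain. A slope-change term recovers it, but only if level and slope are read together. No linear version removes fast early adaptation; the sign of the bias changes instead.

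**The case against.** Four points can be made for the plan, and most of them limit the concern.

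- **The ring does have a reference period.** A reader might infer that there is no ring reading before Somni. The documents do not support that. The ring is worn for three to four weeks before Somni, and component 4 names Weeks 1-4 as the comparison for physiologic metrics. Only the baseline survey point lacks a ring value. This stands, but it leaves component 4 and Aim 3 in conflict, with Week 4 counted twice.
- **The missing point does not cause the drift bias.** This stands. The bias comes from an untrended before/after contrast without a comparison group. The Weeks 1-4 contrast has the same four-week gap.
- **Nights need not be wasted.** A reader might infer that most nights go unused. That depends on a window the plan leaves undefined. Two 7-night windows use 14 of 56 nights (75% unused), three use 21 (62.5% unused), and whole-period means use all (0% unused).
- **A trend model is no cure, and the aim is exploratory.** This stands in part. Kit use, timing and duration are the participant's choice, so gradual uptake is plausible, and a step with one common trend would be a poor sole estimate. Ring sleep is not the primary outcome, which the Aim 1 analysis gives as stress. That is a reason to show both contrasts and to keep claims modest, not to keep a test that lacks one of its points.

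**Conclusion.** The concern holds in a limited form. As written, the ring comparison in Aim 3 lacks a value at one of its three points, disagrees with component 4 about the comparison, and does not isolate a change at the start of Somni. With no comparison group and no trend term, steady drift is passed on at about four times its weekly rate.

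The factor of four follows from the schedule. The drift of 1 to 3 minutes per week, and hence the 4 to 12 minutes, is assumed; the documents do not show that drift will occur. The rejection rates and standard errors rest further on the assumed sample size and SDs and on independent nights. They show how large the problem could be and do not predict this trial's results.

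The matter deserves correction before analysis because the nightly data are already to be collected. It does not threaten the study's other aims.

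**What to change.** 1. Reconcile Study Design, component 4, with the Aim 3 analysis: state one comparison for ring measures and put Week 4 in one period.
2. Keep the three-point comparison for survey measures only. App sleep ratings and kit use also have no baseline value, because Somni begins in Week 4, and should be summarised within the Somni period.
3. Analyse ring sleep duration, and HRV in the same way, with one mixed model on all recorded nights: nurse random intercept, nurse random before/after change, and the contrast at the Somni start with its 95% interval. Define the start. The documents name no recorded start date, so either record one for each nurse or use the scheduled date.
4. Beside that contrast, report a version with a pre-Somni trend plus level and slope change, reading the last two together. Claim a Somni signal only in light of both versions.
5. State that a linear trend does not remove non-linear adaptation to the ring or rota effects, and plot mean sleep by study night so that such patterns can be seen.

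The cost is SAP wording and two fits per ring measure, with no new data or visits. The trend-adjusted interval is wider (SE about 7.1 against 5.1 minutes under the stated assumptions), and wider still if trends differ between nurses.
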